### **Exclusion Criteria:**

- Parent or legal guardian unwilling to participate or understand and sign the provided informed consent
- Known coagulation defect
- Patients on longstanding NSAID therapy
- Known renal impairment

## **11. Vulnerable Populations**

Females that are pregnant or believe to be pregnant, will not be considered for participation in the study, due to medical contraindications.

Cognitively Impaired children will not be considered for participation in the study.

## **12. Local Number of Participants**

We will enroll a total of 120 participants for this study.

## **13. Recruitment Methods**

- Both the Principal Investigator and study staff will take initiative to search for potential study candidates on Epic.
- Potential patients will be identified on Epic via surgery status board. Patients who are undergoing adenotonsillectomy will be approached by study staff prior to their procedure.
- No flyers, advertisements or social media/online recruitment mechanisms will be used to recruit patients.

## **14. Withdrawal of Participants**

Parents or Legal Authorized Representative may withdrawal participant from study without penalty at any given time.

A participant may be withdrawn from study if their surgery is scheduled after hours, or if they do not receive paralytic.

Principal Investigator may withdrawal subject at her discretion as deemed fit for patient safety.

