## **6. Procedures Involved**

After consent has been obtained, patients will be randomly assigned to ketorolac group or non-ketorolac group. All patients will receive a similar anesthetic with inhalational induction with the exception of the ketorolac group receiving 0.5mg/kg IV ketorolac at the end of the procedure once hemostasis has been achieved. The PACU nurses, who will be blinded to ketorolac administration, will evaluate the patients using FLACC scores at 10 minutes post-op, 20 minutes post-op and at time of PACU discharge. For patients with a FLACC score of 6-10, morphine 0.05mg/kg will be administered. For patients with FLACC scores of 3-5, morphine 0.025mg/kg will be administered. The total amount of opioid required to obtain a FLACC score of less than 3 will be evaluated as the primary outcome. The secondary outcomes to be evaluated will be PACU FLACC scores, time required in PACU, incidence of post-tonsillectomy bleeding and total pain medications administered during hospital admission.

All patients will undergo inhalational induction with Nitrous Oxide and Sevoflurane. After IV placement, propofol 1-3mg/kg and fentanyl 1mcg/kg will be administered prior to intubation. Immediately after induction, dexamethasone 0.5mg/kg and an IV infusion of acetaminophen 15mg/kg will be administered. During the intra-op course, dexmedetomidine 0.5mcg/kg and odansetron 0.1mg/kg will be given. Patients in the ketorolac group will receive 0.5mg/kg IV, while those in the non-ketorolac group will not receive any.

A rescue dose of Fentanyl 0.5-1mcg/kg IV will be available for administration at the end of the procedure. The decision to administer this will be left to the discretion of the attending anesthesiologist for the case. The choice to give this will be made based on variables including patient's condition and a 20% increase in the heart rate and blood pressure. In PACU, nurses will be blinded to ketorolac administration, but will be informed of all other medications given.

---

**Protocol Title:** Ketorolac as a Strategy for Reducing Post-Operative Opioid Requirement in Children with OSA undergoing Adenotonsillectomy: A Randomized Controlled Trial

---

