## **7. Statistical Analysis Plan**

Descriptive statistics will be calculated for all variables of interest and will include means and standard deviations, medians and ranges, or counts and percentages, as appropriate. Characteristics of subjects who received ketorolac will be compared to those who did not receive ketorolac using Chi-square tests for comparisons of categorical variables (i.e. gender, race, etc.) and two-sample tests or Mann-Whitney tests for continuous variables (i.e. age, apnea hypopnea index, etc.). For binary outcomes, such as post-tonsillectomy bleeding, cohorts will be compared using Chi-square tests. Generalized linear models will be used to compare differences in amount of narcotic among the two tonsillectomy cohorts, adjusting for any differences in patient and surgical characteristics that may exist between the two groups. Statistical significant will be performed using Stata v. 13.1 (College Station, TX).

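### Section 14 allows a child who receives no paralytic to be withdrawn, ordinarily after randomisation, and Section 7 does not say whether withdrawn children are analysed

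*Combined protocol and SAP*

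**What the plan says.** - **The rule.** Section 14 (Withdrawal of Participants): "A participant may be withdrawn from study if their surgery is scheduled after hours, or if they do not receive paralytic". The wording is permissive. It names no decision-maker or deadline, and does not say what happens to the child's data. Section 14 also allows withdrawal by the parent and, for safety, by the principal investigator.
- **Eligibility.** Neither the inclusion nor the exclusion list in Section 10 mentions a paralytic. Nor does Section 11.
- **Regimen.** Section 6 (Procedures Involved) describes intubation: "After IV placement, propofol 1-3mg/kg and fentanyl 1mcg/kg will be administered prior to intubation". The other drugs it lists are nitrous oxide, sevoflurane, dexamethasone, acetaminophen, dexmedetomidine and ondansetron. No paralytic is named, and none is forbidden.
- **Order of events.** Section 6: "After consent has been obtained, patients will be randomly assigned to ketorolac group or non-ketorolac group". Section 22 places consent before surgery, in clinic or on the day. Section 23 has the pharmacy dispense after randomisation. The ketorolac group is described as "receiving 0.5mg/kg IV ketorolac at the end of the procedure once hemostasis has been achieved".
- **Who knows the arm.** Section 6: "Patients in the ketorolac group will receive 0.5mg/kg IV, while those in the non-ketorolac group will not receive any". No placebo is described. Blinding is stated only for the recovery nurses: "In PACU, nurses will be blinded to ketorolac administration, but will be informed of all other medications given".
- **Analysis.** Section 7: "Characteristics of subjects who received ketorolac will be compared to those who did not receive ketorolac". For the morphine comparison: "Generalized linear models will be used to compare differences in amount of narcotic among the two tonsillectomy cohorts". It gives no analysis set and no rule for withdrawn participants.

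**The concern.** The protocol contradicts itself on this drug. If a paralytic is part of the intended anaesthetic, Section 6 is incomplete. If it is not, Section 14 penalises adherence to Section 6. Either way a discretionary exit opens at a point when the child has ordinarily been assigned already.

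What follows depends on a question the plan leaves open: whether a withdrawn child still counts in the comparison. If not, the trial loses children it has randomised, and the documents state no dropout allowance or power calculation that would absorb the loss. The choice of whom to count could also be made after morphine use is known, by staff who are not stated to be blinded. Readers could then not tell whether the result compares the groups as randomised.

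**Working it through.** **Timing.** The sequence in Sections 22, 6 and 23 is consent, randomisation, dispensing, anaesthesia and surgery, then ketorolac at the end. A paralytic for intubation or surgery falls after assignment and before ketorolac. Two things follow. Non-receipt would ordinarily be known only after randomisation, although the text does not rule out randomising after induction. And ketorolac itself cannot bring about non-receipt.

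**Inputs.** The only figure from the documents is the total of 120 (Sections 1 and 12). There is no alpha, power, SD, allocation ratio or withdrawal rate, so the plan has no figure of its own to reproduce. Everything else here is assumed: 60 per arm, two-sided 5%, normal approximation, 80% power at 60 per arm, withdrawn children dropped and not replaced.

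**Precision, equal losses, constant SD.** With n left per arm, SE ratio = √(60/n), and power = P(Z > 1.96 − 2.802·√(n/60)).

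| Dropped of 120 | n per arm | SE ratio | Power |
|---|---|---|---|
| 6 | 57 | 1.026 | 78% |
| 12 | 54 | 1.054 | 76% |
| 24 | 48 | 1.118 | 71% |

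**Bias.** Drop k₁ and k₂ of 60, with the dropped children's mean d SD from their arm mean, in the same direction in both arms. Then

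- shift = k₁d/(60−k₁) − k₂d/(60−k₂)
- SE = √(1/(60−k₁) + 1/(60−k₂)), in SD units
- r = shift/SE
- false-positive rate = P(Z > 1.96 − r) + P(Z < −1.96 − r)

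| k₁ v k₂ | d | Shift (SD) | SE | r | False-positive rate |
|---|---|---|---|---|---|
| 6 v 6 | 1 | 0 | 0.192 | 0 | 5.0% |
| 4 v 2 | 0.5 | 2/56 − 1/58 = 0.018 | 0.187 | 0.099 | 5.1% |
| 6 v 3 | 0.5 | 3/54 − 1.5/57 = 0.029 | 0.190 | 0.154 | 5.3% |
| 6 v 0 | 1 | 6/54 = 0.111 | 0.188 | 0.592 | 9.1% |

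**Limit of the bias table.** Even use means removing the same kind of child in both arms, not merely the same number. If 6 per arm were removed from opposite ends (d = +1 and −1), the shift would be 6/54 + 6/54 = 0.222 SD, r = 0.222/0.192 = 1.155, and the false-positive rate about 21%. That pattern needs selection that depends on the arm, so it is another extreme form of uneven use.

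**The case against.** The best defence has four parts.

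1. **Section 7 does not exclude anyone.** A reader might infer that withdrawn children are removed from the analysis. The documents do not say so: leaving the study need not mean leaving the analysis. This stands. The defect is silence, and every figure above is conditional on dropping.
2. **The primary comparison is not stated to be as-treated.** A reader might infer this from "Characteristics of subjects who received ketorolac will be compared to those who did not receive ketorolac". That sentence governs the comparison of subject characteristics, and Section 6 forms the groups by random assignment. This also stands, although the model sentence does not say that its cohorts are the assigned groups.
3. **The rule does not in itself bias the trial.** A reader might infer that any exclusion after randomisation must. Here the trigger precedes the study drug, and even-handed removal leaves the expected difference among the remaining children unbiased. Bias needs assignment before the event, someone who knows the arm, uneven use, and dropped data. The documents leave room for this but do not report it.
4. **There may be a rationale.** Section 6 aims for a similar anaesthetic in all patients, and a routine drug may simply have been left off the list. That is plausible, and it would make the point partly one of drafting. Keeping these children may raise the SD a little, so the precision regained could be less than the table implies. It does not explain why a departure in technique should end participation rather than be recorded as a deviation.

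The after-hours trigger in the same sentence adds little: only elective cases are eligible, and Section 22 keeps emergent and urgent cases from being approached.

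**Conclusion.** The point holds as an inconsistency between Sections 6, 10 and 14, joined to an omission in Section 7. A discretionary withdrawal trigger has no basis in eligibility or regimen, would ordinarily arise after randomisation, and has no stated consequence for the analysis.

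Its size is unknown because the documents give no expected number of children without a paralytic. If such children are dropped, the likely effect is the modest precision loss in the first table, over an assumed range of 6 to 24 children. Mild uneven use barely moves the false-positive rate; material bias needs strongly arm-dependent removal, for which the documents give no evidence. A claim that the morphine result will be biased, or that the plan discards these children, would go beyond the text. Label: cheap improvement.

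**What to change.** 1. **Section 14:** delete non-receipt of a paralytic as a reason for withdrawal.
2. **Section 6:** if a paralytic is intended, name it in the regimen and record non-receipt as a protocol deviation.
3. **Sections 7 and 14:** state that every randomised child with usable data, and no withdrawal of consent for data use, is analysed in the assigned arm. This also covers withdrawals by the parent or the principal investigator.
4. **Section 7:** define the groups by assignment instead of by receipt of ketorolac.

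The cost is a short amendment and slightly more heterogeneity in anaesthetic technique. The time of randomisation and the pharmacy workflow can stay as they are. Making the paralytic a required step, or randomising after it is given, would also close the gap, but the second would change when randomisation and dispensing happen.

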## **15. Risk to Participants**

The drug that is being tested may not work any better than regular care. 1-10% of patients that take Ketorolac may have:

- Nausea
- Abdominal Pain
- Headaches

Serious, less common risks include:

- Post-procedure bleeding, after tonsil removal (3%), in children with OSA (2%)
- Less than (1%): chance of allergic or anaphylactic reaction.

## **16. Potential Benefits to Participants**

The study drug may not work any better than regular care; however, we anticipate less morphine will be administered post-operatively.

## **17. Compensation to Participants**

There will be no compensation provided to participants.

## **18. Data Management and Confidentiality**

Confidentiality will be maintained throughout the entire process from obtaining consent to data analysis. Confidentiality will be maintained by only recording information absolutely necessary to fulfill the study's objectives. Information directly identifying patients (names, addresses, telephone numbers, social security numbers, email addresses, and account numbers) will be excluded from any publication or presentation. In the research database, patients will be identified by their assigned study number. The database, along with the code linking a subject's identity to an assigned number, will be locked in the office of the principal investigator or designee.

If a participant declines to participate in the study, the participant will not be assigned a study ID number and the study coordinators will not collect any data on the participant. If the participant agrees to participate in the study, the participant will be assigned a study ID number and the study coordinators will collect data points pertinent to the study. These procedures will help prevent unauthorized inclusion of the patient's data in the RedCap database.

## **19. Provisions to Monitor the Data to Ensure the Safety of Participants**

Monitoring of Adverse Events (AEs) and Serious Adverse Events (SAEs) is an important aspect of data collection. After enrollment, the principal investigator or designee will collect the adverse experiences from the medical record. The study subjects will be reviewed on a case-by-case basis. The principal investigator will determine the seriousness of each adverse event and

whether or not the event was related to the study. Serious adverse events (life-threatening, requiring intervention) will be reported to the IRB within the guidelines set by the IRB.

After 50% of patients enrolled have undergone surgery, evaluation of the rates of post-tonsillectomy bleeding will be carefully evaluated. If any significant increase is noted, the study will be evaluated by the principal investigator for possible discontinuation.

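### Section 19 states one aggregate bleeding review, at 50% of surgeries, so no stated review of the cumulative rate covers the first or the last 60 or so children separately

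*Combined protocol and SAP*

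**What the plan says.** Section 19 (Provisions to Monitor the Data to Ensure the Safety of Participants) is the only place that mentions discontinuing the trial. It sets the time of the look, "After 50% of patients enrolled have undergone surgery, evaluation of the rates of post-tonsillectomy bleeding will be carefully evaluated", and then the consequence: "If any significant increase is noted, the study will be evaluated by the principal investigator for possible discontinuation". It describes no earlier, later or repeated review of rates.

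The other safety provisions work at the level of the single child or event:

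- Section 19, adverse events: "The study subjects will be reviewed on a case-by-case basis". The principal investigator judges seriousness and relatedness.
- Section 19, serious events: "Serious adverse events (life-threatening, requiring intervention) will be reported to the IRB within the guidelines set by the IRB".
- Section 14: "Principal Investigator may withdrawal subject at her discretion as deemed fit for patient safety".

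Section 12 gives the planned size: "We will enroll a total of 120 participants for this study". Section 15 gives bleeding risks of 3% after tonsil removal and 2% in children with OSA. Section 6 has bleeding recorded and classified by whether it needed surgery. Sections 6 and 23 end data collection at discharge.

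**The concern.** Bleeding is the harm that Sections 3 and 5 give as the reason ketorolac use is still debated, and it is the one harm for which the protocol sets a trial-level trigger. Because Section 15 lists it as a known risk, a single bleed judged alone can look expected. An excess shows only when bleeds are counted cumulatively by arm, and the protocol plans a review of the rate once.

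Followed as written, an early cluster does not bring the look forward, and a raised rate that emerges in the second half does not reopen the question. More children could then be exposed to an excess visible in data the trial already records. The point concerns the number and timing of looks. What counts as an increase at the look is a separate question.

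**Working it through.** **1. The split.** Inputs: 120 children (Section 12) and a look at 50% (Section 19). 0.50 × 120 = 60 before the look; 120 − 60 = 60 after it. The figure 60 is not printed, and this reads the 50% as half of the planned total. Section 6 says "patients will be randomly assigned to ketorolac group or non-ketorolac group" without a ratio. If it is 1:1 (assumed), about 30 ketorolac children fall on each side.

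**2. Why single bleeds are not informative.** At 2% to 3%, the expected number among the first 60 children is 60 × 0.02 = 1.2 to 60 × 0.03 = 1.8. The chance of at least one is 1 − 0.98^60 = 70% to 1 − 0.97^60 = 84%. An isolated bleed is therefore unremarkable, and only the count carries information.

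**3. Illustration of extra looks.** Assumptions, none of them from the protocol except the 3% rate: 60 ketorolac children, every bleed captured, and a yardstick of 3 of 15, 3 of 30 and 4 of 45 ketorolac children at the 25%, 50% and 75% looks. The yardstick serves only to compare schedules and is not a proposed rule.

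With X_n the cumulative count among n ketorolac children and p the bleeding rate:

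- Single look: S = P(X_30 ≥ 3) = 1 − Σ_{k=0..2} C(30,k) p^k (1−p)^(30−k). At p = 10%: 1 − (0.0424 + 0.1413 + 0.2277) = 0.589.
- First flag at 25%: f1 = P(X_15 ≥ 3).
- First flag at 50%: f2 = S − f1.
- First flag at 75%: f3 = Σ_{k=0..2} P(X_30 = k) × P(at least 4 − k bleeds in the next 15).
- Three looks: f1 + f2 + f3 = S + f3.
- Mean ketorolac children treated before a flag (60 if none): 60 − 30S for one look; 60 − 45f1 − 30f2 − 15f3 for three. The difference is 15(f1 + f3).

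| True rate | f1 | f2 | f3 | Flag, one look (S) | Flag, three looks (S + f3) | Mean treated, one look | Mean treated, three looks | Saving |
|---|---|---|---|---|---|---|---|---|
| 3% | 0.009 | 0.051 | 0.016 | 6.0% | 7.6% | 58.2 | 57.8 | 0.4 |
| 6% | 0.057 | 0.211 | 0.081 | 26.8% | 34.9% | 52.0 | 49.9 | 2.1 |
| 10% | 0.184 | 0.405 | 0.131 | 58.9% | 72.0% | 42.3 | 37.6 | 4.7 |

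**4. What each look contributes.** Counts are cumulative, so 3 of 15 guarantees at least 3 of 30. Looks at 25% and 50% together therefore flag exactly as often as the 50% look alone (58.9% at a 10% rate). The 25% look only brings a flag forward. All the added detection, 72.0 − 58.9 = 13.1 points at 10%, comes from the 75% look.

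**5. Incomplete capture.** Suppose, as an illustration, that half of bleeds occur before discharge. A true 10% is then recorded as 5%: flags go from 19% to 25%, and mean ketorolac children treated from 54.4 to 53.0, a saving of 1.4. A true 6% is recorded as 3%, a saving of 0.4.

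**6. A count that is always live.** If the count of 4 stayed live up to 60 ketorolac children, flags at a 3% rate would be about 12.5%, against 7.6% for three fixed looks and 6.0% for one.

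**The case against.** The strongest reply is that safety oversight does not pause between looks. The principal investigator or designee collects adverse events throughout, and serious events go to the IRB. A bleed that needs surgery fits Section 19's description of a serious event. This stands. A reader might infer that the 50% look is the only thing that could stop the trial, or that the trigger lapses afterwards. The documents support neither reading. They name one time point and do not exclude other looks, and the principal investigator or the IRB could act at any time. What remains is that no stated provision asks for the cumulative rate at any other point.

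A second reply is that the benefit is small, and this largely stands. A 10% rate is an illustration that borrows the five-fold adult risk in Section 5. The same sentence says that children under 18 were not at significantly increased risk, so 10% should not be read as an expected rate. At 6% the saving is about 2 ketorolac children even with full capture, and it shrinks if bleeds occur after discharge.

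A third reply is that the gain depends on a yardstick the protocol does not contain. That is true of the percentages, not of the gap in timing. With 30 per arm, a two-sided Fisher test at 0.05 would need 6 versus 0 bleeds (p = 0.024; 5 versus 0 gives p = 0.052). Under that definition the detection figures in the table would not apply. How an increase is defined may matter more than the number of looks, but settling it would still leave a single look.

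**Conclusion.** The point holds in a limited form. Section 19 states one aggregate trigger, at about 60 of 120 children, and the continuing adverse event provisions are not tied to a review of the cumulative bleeding rate. The change is recommended for its low cost; the likely gain is modest. Under the stated assumptions, two further looks raise the chance of a flag by 1.6 points at a 3% rate (7.6 − 6.0), about 8 points at 6% and about 13 points at 10%. Mean ketorolac exposure before a flag falls by about 0.4, 2 and 5 children.

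The textual finding rests on reading the 50% as half of the planned total. The percentages also rest on 1:1 allocation, full capture of bleeds and an illustrative yardstick. They overstate the gain to the extent that bleeds occur after discharge.

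**What to change.** In Section 19, keep the 50% review. Add that the principal investigator or designee will also tabulate and review cumulative post-tonsillectomy bleeding by arm after 25% and 75% of surgeries, from data already collected. State that a flag leads to a review, not an automatic stop, and leave any threshold to the sponsor. Note in the same place that the counts cover bleeding up to discharge only.

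The cost is a short amendment, two extra tabulations and a slightly higher chance of an unnecessary review (7.6% against 6.0% at a 3% rate under the illustration). No new committee, visit or data item is needed, and the sample size and the morphine analysis do not change. A count trigger live at any time is not part of this fix, because it would roughly double unnecessary reviews (about 12.5% against 6.0%).
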